5.2 Inclusion criteria

- Patients who need x-ray imaging for dental diagnosis and/or treatment planning
- Males or females aged older than 21
- Can follow instructions to be positioned into the CT scanner
- Can remain physically immobile during the CT scan acquisition
- Voluntarily sign and date the informed consent

5.3 Exclusion criteria

- Pregnancy
- Patients who are unable to comprehend the risks of the study to provide informed consent
- Extensive dental restorations, maxillofacial prosthesis, or orthopedic hardware that likely may cause artifacts and degrade quality, as determined by the study radiologists.

5.4 Lifestyle considerations

Not applicable

5.5 Screen failures

Patients who sign the informed consent will have satisfied all inclusion and exclusion criteria, and thus, it is unlikely that we will have screen failures. Screen failures could occur if a patient decides to revoke informed consent or provides additional data that changes eligibility assessment. In such cases, we will document relevant information including the reason for screen failure, and the specific criteria that are unmet.

As per the American College of Radiology practice parameters for imaging pregnant patients¹⁹, diagnostic examinations of the head and neck do NOT require verification of pregnancy status, because

they do not directly expose the pelvic/abdominal area, and the scattered dose to the embryo/fetus is negligible. Nevertheless, pregnant patients are excluded from this study, following a markedly conservative approach to radiation safety.

Verification of pregnancy status will be via clinical history and is often sufficient for this examination. For example, women may attest that they cannot reasonably be pregnant, are between regular menstrual periods, or are on long-term birth control. From a scientific viewpoint, uncertainty regarding pregnancy typically exists in the early stages. Given the low radiation doses, the likelihood of effects on the embryo-fetus are negligible.

5.6 *Strategies for recruitment*

- The study will recruit subjects who are seeking dental treatment at the UCLA Dental Center.
- The target population is patients, 21 years and older.
- In this study, we will aim for an approximately equal gender distribution in the three age groups.
- Potential participants will be identified via the UCLA Dental Center Clinics, and participation opportunity will be publicized at these clinics and to relevant providers of dental treatment at the UCLA Dental Clinic via electronic and paper communication.
- Vulnerable populations are NOT a target of this recruitment.
- The subject will receive the standard of care MDCT scan at no charge, typically a \$400 value. The DE-CBCT scan will be done at no charge.
- Participants will be reimbursed for parking at the UCLA School of Dentistry (Visit 1) and the UCLA Ronald Reagan Hospital (Visit 2), approximately \$22 in value.
- Because this study involves an additional visit, participants will receive financial compensation of \$100.

6 STUDY INTERVENTIONS AND ADMINISTRATION

6.1 *Study intervention administration*

6.1.1 *Study intervention description*

The device a Dual Energy-Cone Beam Computed Tomography (DE-CBCT), RCT720, is used to make the images of subjects' dento-alveolar bone. The study's radiologist will evaluate these images to make assessments of jaw bone density at specific sites.

6.1.2 *Administration*

The image will be taken once, preferably on the day of the patient's enrollment into the study.

6.2 *Preparation/Handling/Storage/Accountability*

6.2.1 *Acquisition and accountability*

The investigational device is a CT scanner that will be installed by the manufacturer in the UCLA Oral Radiology Clinic and will be used according to the instructions.

- Investigational Device Description

The RCT720 is intended for 3D computed tomography for scanning hard tissues like bone and teeth. By rotating the C-arm which is embedded with a dual high voltage generator, all-in-one x-ray tube and a detector on each end, cone beam computed tomography(CBCT) images of dental maxillofacial are attained by recombining data from the same level that are scanned

from different angles. The dual energy can be used to obtain the HU value for confirming alveolar bone density.

- Manufacturer: Ray Co., Ltd.
- Trade Name: RCT720
- Common Name: Dental panoramic/tomography and cephalometric x-ray system
- Regulation Name: Computed tomography x-ray system
- Regulation Number: 892.1750
- Device Class: II

The control device is a CT scanner that is already installed at the UCLA Ronald Reagan Hospital for the standard diagnosis. It will be used according to the instructions.

- Control Device Description

The Multi Detector Computed Tomography (MDCT) uses multiple x-ray tubes and detectors to produce tomographic images by recombining coplanar data obtained from different angles.

- Manufacturer: **To Be Established by UCLA Radiology**
- Trade Name: Multidetector Computed Tomography
- Common Name: Whole body computerized tomography X-ray imaging device
- Regulation Name: **To Be Established by UCLA Radiology**
- Regulation Number: **To Be Established by UCLA Radiology**
- Device Class: II

6.2.2 Formulation, appearance, packaging, and labeling

- Investigational Device (RCT720)

- Appearance and Formulation:

[figure not shown]
No.	Label	Function
(1)	Vertical carriage	Device which supports the rotating arm
(2)	CT Detector	Part embedded with a detector used for acquiring the CT imaging where the X-ray penetrating the subject is received then converted into an electrical signal and sent to the controller.
(3)	X-ray generator	Part which generates the X-ray for imaging
(4)	Touch Monitor	Includes functions (height adjustment, alignment beam on/off, product initialization) that can control the basic settings for product operation
(5)	Handle	Part grabbed by the patient to get in position for imaging
(6)	Column	Part which adjusts the product height according to the patient's height
(7)	Base	Part which supports the entire equipment system

- Technical Specifications

[figure not shown]
1) X-ray tube:

- Focal spot dimension: 0.5mm
- Maximum tube voltage (imaging): 50~100kVp
- Target angle: 5°
- Inherent filtration: 0.8mm Al at 50kV
- X-ray tube characteristic curve:

a. Maximum rating chart:
Constant potential high-voltage generator

[figure not shown]

b. Emission & Filament characteristics:

c. Anode thermal characteristics:

Anode Thermal Characteristics

2) High Voltage Generator:

- Power: Single phase 100-240VAC, 50/60Hz
- Power consumption: 2.5kVA Max
- Maximum power: 1.53kW
- Tube voltage and tube current control range:

Modality	Tube Voltage (kV)	Tube Current (mA)	kW (kV x mA)
CT	60~90	4 ~ 17 (Maximum permissible tube current =1.12kW / set tube voltage)	Max 1.12

3) X-ray Controller (Collimator):

Modality	Magnification ratio	Exposure time
CT (Patient)	1.44	~14sec

4) Detector:

Modality	Sensor type
CT (FXDD-0606CA)	Flat panel X-ray sensor Detector pixel size: 119 μ m Pixel Matrix: 1256(W) x 1256(H) Sensing Area : 149.5 (W)x 149.5 (H)mm FOV : 160mm x 100mm(Max.)

5) Console PC main frame:

- OS : Windows 10, 64Bit or higher
- CPU : Intel Dual core or better
- RAM : 8GB or higher
- HDD : 1TB or higher

- Network: Ethernet network
- Display: 32 bit color display or higher
- Resolution : 1366×768 or higher

6) Column:

- Movement range: Column stroke (max and min height difference) 670mm
- Vertical Movement: Powered movement

7) Alignment Beam (for patient positioning):

- Laser Class(by IEC60825-1) : Class I
- Wavelength: 650nm±20nm
- Output : <1mW

8) Software

- Name: RayScan
- Version: Ver 1.0 higher

- Packaging and Labeling:

- Each component of the device will be sealed in a 'bubble wrap' to prevent the damage and packaged in a cardboard box. On the surface of the box and on the main body of the device, the statement "CAUTION-Investigation Device. Limited by Federal Law to Investigational Use" will be posted. Further information on the purpose of the investigation, name and place of business of the manufacturer, distributor, the quantity of contents, and a description of all relevant contraindications, hazards, adverse effects, warnings, and precautions will be included in the labeling.

- Control Device (MDCT)
 - MDCT device already installed and in operation at UCLA Ronald Reagan Hospital. Routine maintenance performed as per institutional and state radiation regulatory agencies.

6.2.3 *Product storage and stability*

- Investigational Device (RCT720)
 - Storage condition
 - 1) Temperature range : -10 ~ 50 °C
 - 2) Relative humidity : 10 ~ 90 %
 - 3) Atmospheric pressure range : 700 ~ 1060 hPa

6.2.4 *Preparation*

- Investigational Device (RCT720)

The following is the instruction for how to use the investigational device. User manual must be referred for the details.

 - 1) Preparation
 - a. Only the trained user can operate the device.
 - b. Before using the product, the user must read the user manual.
 - c. After confirming that all cables are properly connected, connect the device to the power cable.
 - d. Check if the switch and the device are operating properly.
 - 2) Operation
 - a. Turn the power switch to “ON.”
 - b. Turn on the PC and execute ‘RayScans.’
 - c. Click [MWL] on the upper left of the screen and [New] button on the lower right to register a new patient.
 - d. Select the scanning mode and set the desired values for the tube voltage and the tube current.
 - e. After adjusting the height of the device to a patient’s height using the remote control or the touch screen, press the [ready] button on the PC or touch screen.
 - f. When the irradiation switch lightens up in green, press the irradiation switch until scanning is completed. Release the irradiation switch, if emergency occurs.
 - g. In case of an emergency, press the [Emergency] switch located in front of the power switch. To restart, turn the [emergency] switch to clockwise direction, until the pressed power switch pops out.
 - h. When scanning is completed, save the image and exit ‘RayScans.’
 - i. Press the power switch to “OFF” to turn off the power.
 - j. In order to reboot the device, wait 5 to 10 seconds after the device is turned off. Then, press the power switch to the “ON” position.
 - 3) Cautions
 - a. Store in a place where there is no possibility of occurrence of adverse effects due to air pressure, temperature, humidity, ventilation, sunlight, dust, salt, and etc.
 - b. During the use, the device and the patient must be monitored.
 - c. Clean regularly with a neutral detergent and make sure the solution does not enter the device.

- d. Using an antiseptic solution such as ethyl alcohol, disinfect the area directly contacted by the patient.
- e. The device and components must be regularly inspected.

6.3 Measures to minimize bias

This study does not include randomization into control and treatment groups. Each subjects' CBCT scan is used as the control to the investigational DE-CBCT scan.

6.4 Study intervention compliance

Not applicable. The intervention is a CT scan, and does not require adherence beyond the imaging visit.

6.5 Concomitant therapy

No restriction for participation in the study

6.5.1 Rescue medication

Not applicable

7 STUDY INTERVENTION DISCONTINUATION AND PARTICIPANT DISCONTINUATION/WITHDRAWAL

7.1 Discontinuation of study intervention

The intervention (patient imaging) occurs in one visit. The only reason to not do the patient imaging would be new information that changes the inclusion/exclusion. The study team will document relevant information including demographics, reason for discontinuance, and the specific criteria that are unmet. Since the study is a single imaging intervention, discontinuance from the study has no impact on the patient's safety or well-being and requires no further action from the study team.

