7.2 Participant Discontinuation/Withdrawal from the Study

Participants are free to withdraw from participation in the study at any time upon request.

An investigator may discontinue or withdraw a participant from the study for the following reasons:

- Pregnancy
- Significant study intervention non-compliance
- Development of new conditions that would change inclusion/exclusion criteria
- If the participant meets an exclusion criterion (either newly developed or not previously recognized) that precludes further study participation
- Participant unable to receive CT for 30 days.

The reason for participant discontinuation or withdrawal from the study will be recorded on the Case Report Form (CRF).

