 - HA Concentration (mg/cm³): 0, 100, 200, 400, 600, 800, 1000, 1200
 - Calibration protocol: ISO 9001 QM-System
5. Following the calibration, the research staff will acquire a DE-CBCT imaging. Either mandible or maxilla, depending on the tooth number (imaging site), will be imaged. The appropriate imaging mode will be selected depending on patient size and field of view, and the tube energy set at 60 kV / 90 kV. The DE-CBCT will be acquired with the imaging stent in place.
6. Subject will be scheduled for MDCT scan (Visit 2). The next visit must be within 30days after the visit
 1. Depending on the availability of scheduling on MDCT unit, Visit 2 may occur on the same day as Visit 1.
7. Before the patient returns home, the study staff will educate the subject to contact him/her if adverse events such as nausea, vomiting, hair loss, and oral inflammation occur.

Study Procedure: MDCT scan (Visit 2)

1. Patients scheduled for their MDCT imaging procedures will be confirmed by the imaging facility via the name and date of birth and assigned screening number.
2. For women in childbearing age, pregnancy status will be re-confirmed and recorded.
3. The region of interest (example: tooth number, potential implant site) that requires radiographic imaging will be recorded. The imaging site for MDCT scan will be identical to the one for DE-CBCT scan.
4. The patient will be imaged using the standard clinical protocol for MDCT, and simultaneous scanning of the calibration phantom (QRM-BDC/6).

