8.4.2 Serious adverse event

An adverse event (AE) or suspected adverse reaction is considered "serious" if, in the view of either the investigator or sponsor, it results in any of the following outcomes: death, a life-threatening adverse event, inpatient hospitalization or prolongation of existing hospitalization, a persistent or significant incapacity or substantial disruption of the ability to conduct normal life functions, or a congenital anomaly/birth defect. Important medical events that may not result in death, be life-threatening, or require hospitalization may be considered serious when, based upon appropriate medical judgment, they may jeopardize the participant and may require medical or surgical intervention to prevent one of the outcomes listed in this definition.

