8.4.4 Time Period and Frequency for Event Assessment and Follow-Up

All AEs including local and systemic reactions not meeting the criteria for SAEs will be captured on the appropriate case report form (CRF). Information to be collected includes event description, time of onset, clinician's assessment of severity, relationship to study product (assessed only by those with the training and authority to make a diagnosis), and time of resolution/stabilization of the event. All AEs occurring while on study must be documented appropriately regardless of relationship. All AEs will be followed to adequate resolution.

Any medical condition that is present at the time that the participant is screened will be considered as baseline and not reported as an AE. However, if the study participant's condition deteriorates at any time during the study, it will be recorded as an AE.

Changes in the severity of an AE will be documented to allow an assessment of the duration of the event at each level of severity to be performed. AEs characterized as intermittent require documentation of onset and duration of each episode.

The PI or his designee will record all reportable events with start dates occurring any time after informed consent is obtained until 7 (for non-serious AEs) or 30 days (for SAEs) after the last day of study participation. At each study visit, the investigator will inquire about the occurrence of AE/SAEs since the last visit. Events will be followed for outcome information until resolution or stabilization.

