8.4.9 Reporting of pregnancy

Not applicable.

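### Sections 7.1 and 8.4.9 need reconciling with the adverse-event rules for participants who leave after the DE-CBCT, and adverse events should be summarised for everyone scanned, not only per-protocol completers

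*Combined protocol and SAP*

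**What the plan says.** **Discontinuation.** Section 7.1 describes imaging as occurring in one visit and gives one ground for omitting it: "The only reason to not do the patient imaging would be new information that changes the inclusion/exclusion". It concludes that discontinuance from the study has no impact on the patient's "safety or well-being and requires no further action from the study team".

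**Withdrawal.** Section 7.2 begins "An investigator may discontinue or withdraw a participant from the study for the following reasons". Pregnancy is first on the list. Another reason is being unable to receive CT for 30 days. Section 7.3 deals with failure to return for either of two study visits.

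**Visits.** Section 8.1 places the DE-CBCT at Visit 1 and the MDCT at Visit 2: "The next visit must be within 30days after the visit" 1, with the same day allowed. At Visit 2, "For women in childbearing age, pregnancy status will be re-confirmed and recorded".

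**Adverse events.** Section 8.4.2 includes "a congenital anomaly/birth defect" among serious outcomes. Section 8.4.4 states "All AEs will be followed to adequate resolution". It sets recording from consent until 7 days (non-serious) or 30 days (serious) after the last day of participation.

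**Pregnancy.** The entry under "8.4.9 Reporting of pregnancy" is that it does not apply. Section 5.5 calls effects on the embryo or fetus negligible at these doses.

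**Analysis.** Section 3.1 puts safety in the primary objective. Section 9 names one analysis set, per-protocol: participants who finish both scans without a major violation. Image degradation at the region of interest by a metal prosthesis is the listed violation.

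**The concern.** Section 7.1 reasons as if there were one scan. With two scans on separate days, some participants may receive the investigational exposure and then leave. For them, site staff could read 7.1 as ending the team's involvement, while 8.4.4 tells them to continue recording and following events. The pregnancy provisions show a similar gap: the protocol re-checks for pregnancy after the DE-CBCT and lists a birth defect as serious, but states no reporting step that links the two.

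The statistical stake is the safety conclusion. Exposed participants who leave early fall outside the only defined analysis set, and leaving may be related to how a participant fared after the first scan. Even if their events were collected under 8.4.4, no planned analysis includes them.

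**Working it through.** The plan states no figure for this point, so the check is mainly a comparison of sections, with two short calculations.

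**1. Can a participant be exposed and then leave?** Yes.
- Section 8.1 puts the DE-CBCT first and allows 0 to 30 days before the MDCT.
- Section 4.5 requires both scans for completion.
- Sections 7.2 and 7.3 supply routes out in between: a positive pregnancy check at Visit 2, no MDCT obtained in 30 days, the participant's own request, or loss to follow-up.
- Section 7.2 does not itself mention timing. That a pregnancy may first be found after the DE-CBCT follows from the Visit 2 re-check in 8.1.

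**2. What do the sections direct for that participant?**

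| Question | One text | Another text |
|---|---|---|
| Further action after leaving? | 7.1: none | 8.4.4: record for 7 or 30 days, follow all events |
| Pregnancy found at Visit 2? | 7.2: may withdraw, with the reason on the CRF; 8.1: status recorded | 8.4.9: reporting not applicable |
| Birth defect? | 8.4.2: serious | 8.4.9: no reporting step; 5.5: effects negligible, but not cited in 8.4.9 |
| Included in the analysis? | 3.1: safety is part of the primary objective | 9: only the per-protocol set is analysed |

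**3. Reporting window.** For a participant withdrawn at Visit 2, taking that day as the last day of participation, serious-event recording ends at most 30 + 30 = 60 days after the DE-CBCT. The documents give no gestation length. Assuming a term pregnancy of about 260 to 290 days, a birth defect in a pregnancy first detected at Visit 2 would normally appear after the window closes.

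**4. Size of the numerical effect.** Inputs are 24 enrolled and 10% dropout (Section 5.1). Since 24 × 0.10 = 2.4, two or three participants may leave. Three leaves 24 − 3 = 21. With zero events in n participants, the one-sided 95% upper bound on incidence is 1 − 0.05^(1/n):

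- n = 24: 1 − 0.05^(1/24) = 0.117, or 11.7%
- n = 21: 1 − 0.05^(1/21) = 0.133, or 13.3%

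The difference is 1.6 percentage points. The second figure assumes that all three dropouts were scanned and then not followed. The documents do not say when dropout is expected; anyone leaving before Visit 1 was never exposed to the device.

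**5. What the bound does not show.** It measures lost precision, not selection. As a hypothetical, one event among three exposed withdrawals would be 1/24 = 4.2% of those scanned but 0/21 in a completers-only report.

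**The case against.** Section 7.1 is headed as discontinuation of the intervention, and the case it describes is imaging that is not done. The investigational scan does take place in one visit; the MDCT is the standard-of-care control. On that reading, 7.1 covers people who were never scanned, withdrawal belongs to 7.2, and 7.2 contains no such sentence. Section 8.4.4 is the dedicated adverse-event section and already covers withdrawn participants. Section 8.1 also has staff ask participants at Visit 1 to make contact if symptoms occur. For pregnancy, status is recorded at both visits, the withdrawal reason goes on the CRF, and 5.5 gives a rationale consistent with 8.4.9. A general definition of serious events does not by itself create a pregnancy-reporting procedure.

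Much of this stands, and it rules out several stronger conclusions that a reader might draw:

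- *That the sections cannot all be applied together.* Under the narrow reading of 7.1 they can. The conflict depends on the broad reading, which remains open because 7.1 speaks of leaving the study and its trigger, new eligibility information, is what a positive Visit 2 check would be.
- *That exposed withdrawals supply no further safety data.* That requires 7.1 to override 8.4.4, and nothing says it does.
- *That 7.2 obliges withdrawal for pregnancy.* It only permits it.
- *That 7.1 or 8.4.9 causes a completers-only safety conclusion.* That comes from the single analysis set in Section 9.
- *That 8.4.9 alone makes a birth defect unobservable.* The 30-day serious-event window has much the same effect.

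The objection leaves Section 9 untouched, and 8.4.9 does not refer to 5.5.

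**Conclusion.** The point holds as an ambiguity in site instructions together with a gap in the analysis plan. Read broadly, 7.1 conflicts with 8.4.4 for participants who leave between the scans. Section 8.4.9 is not reconciled with 7.2, the Visit 2 re-check and 8.4.2; 5.5 offers a reason but is not linked to it. Section 9 as written leaves exposed non-completers out of the only analysis set, although safety is part of the primary objective.

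The size is modest: at most two or three participants at the planned dropout rate, and at worst a move in the zero-event bound from 11.7% to 13.3%. Sample size, power, the correlation and the Bland-Altman analysis are unaffected. The case for acting is that the change is nearly free and removes a possible selection effect from the safety conclusion. The conclusion assumes that some dropout occurs after Visit 1, which the design allows but the documents do not quantify.

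**What to change.** 1. Reconcile 7.1 with 7.2 and 8.4.4 for participants who leave after the DE-CBCT, so that site staff have one instruction. The text should make clear which participants the sentence in 7.1 concerns.
2. Reconcile 8.4.9 with 5.5, 7.2, the Visit 2 re-check in 8.1 and 8.4.2. The sponsor and IRB should decide the content of any pregnancy follow-up; no clinical rule is proposed here.
3. In Section 9, summarise adverse events for all participants who received the DE-CBCT, not only the per-protocol set. List each exposed withdrawal with the reason, timing and adverse-event status at last contact. This would also retain participants excluded from the per-protocol set only for image quality.

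The cost is protocol wording, one additional denominator and a short listing. Any extra site effort concerns the few participants who leave after Visit 1. No change to enrolment or to the effectiveness analyses is needed.
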